Title: In vivo characterization of the non-genomic effects of T3 on endothelial and cardiovascular function

NCT #: NCT03098433

Document date: 01/19/2017

Document Type: Protocol and Statistical Analysis Plan

In vivo characterization of the non-genomic effects of T3 on endothelial and cardiovascular function

Study protocol

Research Description

Hypothyroidism is a common condition caused by failure of the thyroid gland or as a result of thyroid surgery for benign or malignant lesions. Hypothyroidism is treated by administering levothyroxine (LT4) a synthetic inactive form of the thyroid hormone. This drug is then metabolized by the organism into its active form, T3.

Several lines of evidence indicate that LT4 alone may not be sufficient in assuring adequate tissue levels of T3 and some studies suggest that the addition of liothyronine (LT3) the synthetic form of T3 to LT4 can improve the symptoms and signs associated with hypothyroidism. LT3 has a short half life and it is usually administered in two-three doses daily. There is also evidence supporting the hypothesis that T3 exerts rapid, "non genomic" effects, particularly on the vessels. If this is the case a tight regulation of the LT3 dose to maintain the serum concentration of T3 becomes of primary importance.

To assess the non genomic effect of LT3 we will perform a proof-of-concept, double blind randomized crossover study in twenty healthy volunteers aimed to measure the acute cardiovascular and energy expenditure changes following a single equimolar dose of LT3 or LT4.

Specific aims or goals.

Aim 1: To compare the effects of a single dose of 0.7mcg/kg in liquid formulation (equivalent to a dose of 50 mcg in a 70 Kg individual) of LT3 to an equimolar 0.86 mcg/kg single dose of LT4 in liquid formulation, and to placebo on cardiovascular system. We will record the following parameters: heart rate, blood pressure, cardiac output, flow-mediated dilation.

Aim 2: To compare the effects of a single dose of 0.7mcg/kg of LT3 in liquid formulation to an equimolar single dose of LT4 in liquid formulation, and to placebo on the energy metabolism and substrate utilization. We will record the following parameters: energy expenditure by whole room indirect calorimeter, respiratory quotient, skin and core temperature.

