B) Study visit #1-3. Study participants will be evaluated in the morning after an overnight fast during three consecutive outpatient visits, with at least a 24-hour interval between. Upon arrival to the Clinical Research Service Unit (CRSU) and abbreviated history and physical examination with recording of anthropometrics will be obtained; an i.v. cannula will be inserted in the left arm. Study volunteers will be fitted with electrodes for EKG Holter recording, and a cuff on the third finger of the right hand to record blood pressure and heart rate, cardiac output, systemic vascular resistance and endothelial function. An echocardiogram will be recorded at the beginning and at the end of each study session. Study volunteers will then enter in the whole room ("Flex room") a 4' x 8' x 7' indirect calorimeter with a temperature set at 24°C and rest on a bed. The Flex room has a window and a TV monitor, and is connected to the nursing station via an interphone system. An i.v. port is located on the door of the Flex room allowing drawing of samples without compromising the recording of energy expenditure. After 40 minutes (time 0'), study volunteers will receive either 0.7mcg/kg (equivalent to a dose of 50 mcg in a 70 Kg individual) of LT3 to an equimolar 0.86 mcg/kg single dose of LT4, and to placebo in liquid form. The doses were chosen to be within the usual therapeutic range prescribed in preparation for radioiodine ablation. Blood samples will be obtained at the following time points: 0', 60' 120' 180' 240' for total and free T3, total and free T4, TSH and 500 μ l aliquots of serum TSH will be recorded at times 0' and 240' of each Study visit. Energy expenditure and respiratory quotient will be recorded throughout the duration of the stay in the Flex room. The first 20 minute of the recording will be discarded to allow for equilibration. At the end of the session the i.v. cannula will be removed, vital signs recorded and the volunteer will be discharged provided with a coupon for a meal in the hospital cafeteria. The same procedures will be repeated in the identical order and timing for the other formulations.

Justification for the sample size:

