The primary analysis will be performed by two-tailed paired t-test with an 0.05 α error as a threshold for statistical significance on the assumption that LT3 administration, compared to LT4 will result in a 30% increase in FMD, corresponding to 0.75 SD. Using this experimental conditions and assumptions, a 20 volunteers will provide 88% power to detect a significant difference, while assuming a 20% drop-out rate the power will be 80%.

List the study inclusion criteria:

Healthy volunteers, both sexes

Age range 18-45 year

Body Mass Index range 20- 30 kg/m²

Ability to provide informed consent to the participation in the study

List the study inclusion criteria:

Abnormal TSH (>0.5<5.0 mIU/mL)

Thyroid disease or autoimmunity by history or anti-thyroid peroxidase (TPO) antibodies.

Pregnancy or lactation

Chronic use of prescription drugs

Diabetes mellitus (by history or fasting glucose >126 mg/dl)

Dyslipidemia (total cholesterol >240 mg/dl)

Hypertension (by history or screening systolic blood pressure > 140 mm/Hg, and/or diastolic blood pressure > 90 mm/Hg)

Cardiac arrhythmia (by history or screening EKG)

Anemia (Hb<13.3 g/dl M, 12.0 g/dl F)

Renal insufficiency by history or estimated creatinine clearance ≤ 60 mL/min/1.73m² BSA.

Liver disease or transaminases >2.5 x the upper laboratory reference limit.

Current tobacco use.

Criteria for withdrawing an individual participant from the study:

Volunteers may withdraw from the study at any time. The investigators can withdraw any volunteer at any time from the study if medically necessary.

Medical reasons for withdraw from the study:

- 1) Tachycardia (heart rate greater than 100/min)
- 2) Anxiety
- 3) Development of hypertension (systolic >160 mmHg, diastolic > 90 mmHg) following administration of the study drug
- 4) Development of hypotension (systolic <90 mmHg, diastolic < 60 mmHg) following administration of the study drug

Adverse events mitigation:

All AEs and SAEs will be followed until resolution, until the condition stabilizes, until the event is otherwise explained, whichever occurs first. All AEs and SAEs documented at a previous visit/contact

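### The only stated test, a complete-pair t-test, leaves measured visits unused and has no rule for withdrawn volunteers, although most medical withdrawal reasons are limits on Aim 1 outcomes; the main cost is power.

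*Combined protocol and SAP*

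**What the plan says.** Under Justification for the sample size, the plan states: "The primary analysis will be performed by two-tailed paired t-test". The comparison is LT3 against LT4 on FMD, at a two-sided 0.05 level, with an assumed effect of 0.75 SD. Twenty volunteers are said to give 88% power, and then "assuming a 20% drop-out rate the power will be 80" (per cent). No other test is named.

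Under Criteria for withdrawing an individual participant from the study, the plan says: "The investigators can withdraw any volunteer at any time from the study if medically necessary". It then lists four medical reasons. One is anxiety. The other three are "Tachycardia (heart rate greater than 100/min"), "Development of hypertension (systolic >160 mmHg, diastolic > 90 mmHg) following administration of the study drug" and "Development of hypotension (systolic <90 mmHg, diastolic < 60 mmHg) following administration of the study drug".

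Aim 1 says: "We will record the following parameters: heart rate, blood pressure, cardiac output, flow-mediated dilation". Study design, part B, describes three visits at least a day apart, one each for LT3, LT4 and placebo, and a finger cuff "to record blood pressure and heart rate, cardiac output, systemic vascular resistance and endothelial function".

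No section defines an analysis set, replacement of withdrawn volunteers, the use of their completed visits, or the handling of a session that is cut short. The text on adverse events concerns their follow-up, not the analysis.

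**The concern.** A paired t-test uses a volunteer only if both the LT3 and the LT4 value exist. A volunteer who stops at visit 1 or 2 loses the later treatments, and usually the pair with them. What was measured on that volunteer is then unused, as are the placebo visits of everyone else. The test also has no period term, although this is a three-visit crossover.

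Because three withdrawal reasons are limits on outcomes the trial compares, and the two pressure reasons apply after dosing, the missing data need not be a random subset. With 20 volunteers, a few exclusions matter. Whether a triggering visit is kept or dropped could be settled after the data are seen. At stake are some power for FMD and the interpretability of the blood-pressure and heart-rate comparisons.

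**Working it through.** **1. The plan's own power.** Inputs, all from Justification for the sample size: effect 0.75 SD, two-sided 0.05, paired t-test. The text does not say which SD is meant; reading it as the SD of the paired difference reproduces both stated figures. Power comes from the non-central t distribution with n − 1 degrees of freedom and non-centrality 0.75 × √n.

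- n = 20: 0.75 × √20 = 3.35, power 88.9% (stated 88%).
- n = 20 × 0.8 = 16: 0.75 × √16 = 3.00, power 80.1% (stated 80%).
- n = 15: 77.1%. n = 14: 73.7%.

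So the stated 80% is the power of 16 complete pairs, with no replacement and no use of partial data.

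**2. What random drop-out costs.** Assumptions, not in the documents: six treatment orders with 3 or 4 volunteers each, SD of the paired difference 1, intraclass correlation 0.5, and a drop-out's last visit equally likely to be visit 1 or 2. A drop-out keeps the LT3–LT4 pair only by completing two visits that happen to be those two treatments: 1/2 × 1/3 = 1/6.

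- 4 drop-outs: 16 + 4/6 = 16.7 pairs on average. They supply 4 × 1.5 = 6 measured visits, of which 2 × 4/6 = 1.3 enter the test.
- 6 drop-outs: 14 + 6/6 = 15.0 pairs.

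Simulated power for FMD, paired t-test against a mixed model (treatment and period fixed, volunteer random, REML with Kenward-Roger degrees of freedom):

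| Drop-outs | No period trend | Trend of 0.3 SD per visit (assumed) |
|---|---|---|
| 0 of 20 | 89% vs 90% | 85% vs 90% |
| 4 of 20 | 82% vs 85–86% | 76% vs 85–86% |
| 6 of 20 | 77% vs 82% | 71% vs 82% |

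A more conservative model with volunteer as a fixed effect gave about 84–85% against 82% with 4 drop-outs, and 81% against 77–78% with 6. The gain without a trend is therefore about 2 to 5 points.

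The trend hurts the paired test because LT3 and LT4 are one visit apart in two-thirds of orders and two apart in one-third. This adds 0.3² × (2/3 × 1 + 1/3 × 4) = 0.18 to the variance of the differences, raising their SD from 1 to √1.18 = 1.09.

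**3. Bias in FMD.** If 20% are lost and the trigger has correlation r with the volunteer's LT3–LT4 FMD difference, the complete-pair mean shifts by −0.35 × r SD. That is 0 at r = 0 and about 0.105 at r = ±0.3, in either direction. The documents give no r. Tying loss to diastolic pressure (assumed mean 70 or 75, between-person SD 7, visit SD 4, LT3 effect −5 mmHg, FMD–diastolic correlation −0.5 to +0.5, every trigger acted on) gave these estimates of the true 0.75:

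- FMD measured before the stop: 0.73–0.77 (pairs), 0.74–0.76 (mixed model).
- FMD missing at that visit: 0.69–0.81 for both.

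The largest shift, 0.06, is a quarter of a standard error of 0.24.

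**4. Blood pressure.** With four readings per visit, an assumed diastolic effect of −5 mmHg and every trigger acted on, complete pairs gave −3.4 to −4.1 if the triggering visit is discarded, but −5.0 to −5.6 if its last reading is used. The direction depends on the handling rule. With the visit discarded, the mixed model was worse than pairs (−2.9 to −3.8). On individual readings it gave −5.0 when the effect was constant over the session. When the effect grew (0, −3.3, −6.7, −10; mean −5), a model without a treatment-by-time term gave −4.40 to −4.68; adding the term restored −4.97 to −5.03. These models used the true variance components, so their small-sample error rate is unchecked.

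**The case against.** The plan does not forecast 20% loss; it assumes it as a power scenario. A complete-pair analysis without replacement is implied by the 80% figure, so loss is partly handled. That stands: the gap is the missing explicit rule and the unused data.

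A reader might infer that the primary FMD result is biased. The documents do not support that. No withdrawal reason refers to FMD, withdrawal is discretionary, and no link between FMD and the limits is given. If FMD is missing at the stopped visit, the mixed model has the same bias as pairs.

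A reader might also infer that blood-pressure effects would be understated by some definite percentage. That fails too: every input is external, the sign changes with the handling rule, and acting on every trigger in the four-reading case withdraws 36–67% of volunteers, far above the planned 20%. The plan does not say which readings count, or state a test for blood pressure.

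For a 20-person proof-of-concept study, 2 to 5 points of power is modest, and larger gains need an assumed period trend. That is fair, and it limits the weight of the point. It does not remove it, because the better analysis needs no new data.

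**Conclusion.** The concern holds in a limited form. Three of four medical withdrawal reasons are limits on Aim 1 outcomes, and the only stated test has no rule for the resulting partial data. The stated power figures are correct for 20 and 16 complete pairs; a reader who took the point to mean they are wrong would be mistaken. They do presuppose that loss is unrelated to the FMD response and no greater than 20%.

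For FMD, the cost is mainly power: about 2 to 5 points at 4 to 6 random drop-outs, and about 9 to 11 points under the assumed period trend. Bias is probably small and of unknown direction. For blood pressure and heart rate, neither direction nor size can be fixed from the documents. All simulated figures rest on the assumptions listed with them. This is a cheap improvement for the sponsor to consider, not an error that invalidates the plan.

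**What to change.** Analysis wording only; withdrawal decisions are unchanged.

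1. Keep all data recorded up to and including the reading that led to withdrawal, for every outcome measured by then.
2. Make the primary FMD analysis a mixed model with treatment and period fixed and volunteer random (REML, Kenward-Roger) on all available LT3, LT4 and placebo visits. LT3 minus LT4 remains the primary contrast, and the complete-pair t-test becomes a sensitivity analysis.
3. If blood pressure and heart rate are modelled on individual timed readings, include a treatment-by-time term. Do not use the mean or last value of a visit that was cut short.
4. Report withdrawals by treatment, period and reason.

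Item 1 must accompany items 2 and 3, since discarding the triggering visit made the mixed model worse than pairs for blood pressure.

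Separately, the two pressure limits are joined by a comma and can be read as requiring both readings or either one. The hypertension exclusion criterion spells this out; the withdrawal list does not. The sponsor should clarify it. No threshold is proposed here.

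The cost is SAP text, a mixed model for each outcome type and one sensitivity analysis, with no new visits, procedures or volunteers. Downsides: the models rely on data being missing at random; false positives for FMD may slightly exceed 5% (up to about 5.9% in simulation, against 3.7–5.7% for the paired t-test); FMD not measured at a stopped visit stays missing, with the same bias as complete pairs; and carry-over is not addressed.
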